#### 10.3.2 Part B

Safety pharmacology studies have shown that DNDI-0690 had no effects on CNS, respiratory function, and cardiovascular system. The absence of any effect on cardiovascular system was confirmed in vivo in the telemetry study in conscious cynomolgus monkeys, where no effects on cardiovascular parameters and body temperature were seen up to the single dose of 350 mg/kg.

There were no clinically significant findings in ECG results and no notable increases in QTcF interval in the SAD healthy volunteer study up to 3600 mg.

However, some heart changes as a consequence of nephrotoxicity were considered agonal in their nature and contributory to death together with renal changes in animal studies.

- Therefore, circulating levels of troponin I will continue to be monitored in the MAD study in healthy subjects at admission, at last day of treatment and in case of any ECG clinically significant abnormality during the course of treatment.
- In addition to safety ECGs, the effect of DNDI-0690 on Holter ECG parameters will be assessed in Part A and Part B.

Part B will only be implemented if the cardiac pharmacodynamic assessment (supratherapeutic dose) is needed and if the SRC considers safe to proceed to a daily dosing above 2400 mg (with a maximum allowed dose of 3600 mg).

#### 10.3.3 Part C

In line with the FDA's draft guidance for industry (U.S. Department of Health and Human Services 2017), additional evidence from clinical mechanistic studies is required in order to confirm whether or not the elevations in serum creatinine observed in the SAD study are due

DNDi RD 777/34920 DNDi- 0690- 02

Final V3.0/ Date 07 December 2020

Confidential

Page 53 of 109

to inhibition of the MATE-1 or other transporters. To address this, once a maximum tolerated dose of DNDi-0690 will be identified or at the highest dose tested, a cohort to calculate measured glomerular filtration rate (mGFR) will be conducted. mGFR data will be used for assessment of renal function. In the mGFR cohort, 9 subjects will receive multiple doses of DNDI-0690 or placebo once daily in a similar study design to the Part A cohorts, with the following specificities:

- Dose in Part C will already have been explored, no sentinel group will be implemented in this cohort.
- All subjects will receive 5 mL of iohexol solution (300 mg/mL iodine) intravenously on Day -1, Day 10, and optionally Day 24-28 that will be flushed with 10 mL of normal saline solution. On Day -1, iohexol will be administered at the same time as expected dosing of study drug on Day 10. On Day 10, iohexol will be administered immediately after dosing of study drug.
- Precaution for use as per iohexol summary of product characteristics (SmPC) will be respected.

## 10.4 Selection of Study Population

Up to fifty-four (54), 6 cohorts of 9 healthy male and healthy WONCBP subjects will be required to complete the study.

The study is to be conducted in healthy subjects; therefore, participants are not expected to derive any therapeutic benefit from taking part in the study. A healthy subject population with carefully considered inclusion / exclusion criteria will avoid the potential for interaction of DNDI-0690 with any underlying disease state or concomitant medication that it may be necessary for patients to take, while ensuring that subjects are fit and well enough for participation in the study.

The following eligibility criteria are designed to select subjects for whom protocol treatment and procedures are considered appropriate. All relevant medical and non-medical conditions should be taken into consideration when deciding whether this protocol is suitable for a particular subject.

Deviations from inclusion and exclusion criteria are not allowed as deviations have the potential to impact the scientific integrity of the study, regulatory acceptability or participant safety as such deviations constitute a deliberate breach of Regulation 29 of SI 2004/1031. Therefore, adherence to the criteria as specified in the protocol is essential.

#### 10.4.1 Inclusion Criteria

To be confirmed at Screening:

- 1. Healthy males or healthy women of non-childbearing potential (WONCBP) between 18 and 55 years of age inclusive at the time of signing informed consent.
- 2. Female subject of non-childbearing potential. WONCBP is defined as women who are postmenopausal or permanently sterilised (permanent sterilisation methods include hysterectomy, bilateral salpingectomy, and bilateral oophorectomy).

DNDi RD 777/34920 DNDi- 0690- 02

Final V3.0/ Date 07 December 2020

Confidential

Page 54 of 109

- 3. Female post-menopausal state is defined as no menses for 12 months without an alternative medical cause and confirmed by a serum FSH result of  $\geq$ 40 IU/L at Screening.
- 4. Male subject (and subject's partner of childbearing potential) must use condom and also willing to use a highly effective method of contraception or 2 effective methods of contraception (see Section 10.5.2), if applicable (unless anatomically sterile or where abstaining from sexual intercourse is in line with the preferred and usual lifestyle of the subject) from first dose until 3 months after last dose of IMP.
- 5. Body mass index (BMI) of 18.0 to 30.1 kg/m2 as measured at Screening and body weight  $\geq$ 60 kg (BMI = body weight (kg) / [height (m)]).
- 6. No clinically significant abnormal test results for serum biochemistry, haematology and/or urine analyses within 28 days before the first dose administration of the IMP.
- 7. Subject with a negative urinary drugs of abuse (DOA) screen (including alcohol and cotinine) test results, determined within 28 days before the first dose administration of the IMP (N.B.: A positive test result may be repeated at the Investigator's discretion).
- 8. Subject with negative human immunodeficiency virus (HIV), hepatitis B surface antigen (HBsAg)) and hepatitis C virus antibody (HCV Ab) test results at Screening.
- 9. General good physical health determined by medical and surgical history, physical examination, 12-lead ECG, vital signs and clinical laboratory tests.
- 10. Normal blood pressure: Systolic blood pressure between ≥90 and ≤140 mmHg, Diastolic blood pressure ≤90 mmHg, measured after 10 min rest in supine position at Screening, admission and pre-dose.
- 11. A resting heart rate (HR) between ≥50 and ≤100 bpm measured after 10 min rest in supine position at Screening, admission and pre-dose.
- 12. ECG recording without clinically significant abnormality, including QTcF measure of ≤450 msec at Screening, admission and pre-dose.
- 13. No febrile seizures or infectious illness for at least 7 days prior to first administration of the IMP (Day 1).
- 14. Must agree to adhere to the contraception requirements and the life-style restrictions
- 15. Subject must be available to complete the study (including all follow up visits).
- 16. Subject must satisfy an Investigator about his/her fitness to participate in the study.
- 17. Subject must provide written informed consent to participate in the study.

### To be re-confirmed on Day -2:

- 1. Subject continues to meet all Screening inclusion criteria.
- 2. Subject with a negative urinary DOA screen (including alcohol/cotinine) prior to first dose administration.

Confidential

Page 55 of 109

DNDi RD 777/34920 DNDi- 0690- 02

### Final V3.0/ Date 07 December 2020

#### 10.4.2 Exclusion Criteria

### To be confirmed at Screening:

- 1. Subjects who have received any IMP in a clinical research study within 90 days prior to Day 1.
- 2. Subjects who are study site employees, or immediate family members of a study site or sponsor employee.
- 3. Subjects who have previously been enrolled in this study and/or have received DNDI-0690 previously.
- 4. History of any drug or alcohol abuse in the past 2 years.
- 5. Demonstrating excess in caffeine/xanthine consumption (more than 6 cups of coffee or equivalent a day).
- 6. Regular alcohol consumption in males >21 units per week and females >14 units per week (1 unit = ½ pint beer, or a 25 mL shot of 40% spirit, 1.5 to 2 Units = 125 mL glass of wine, depending on type). As confirmed by a positive urine alcohol test at Screening or admission.
- 7. Current smokers or those who have smoked within the last 12 months with a positive cotinine result at Screening and Admission.
- 8. Current users of cigarette replacements (*i.e.* e-cigarettes, nicotine patches or gums) and those who have used these products within the last 12 months.
- 9. Subjects who do not have suitable veins for multiple venepunctures/cannulation as assessed by the Investigator or delegate at Screening.
- 10. Clinically significant abnormal biochemistry, haematology, coagulation or urinalysis as judged by the Investigator or AST/ALT/total bilirubin/gamma glutamyl transpeptidase [GGT]/ALP/creatinine > 1.2 ULN. Subjects with Gilbert's syndrome are allowed.
- 11. Positive PCR COVID-19 test at admission.
- 12. Evidence of renal impairment at Screening or admission, as indicated by an estimated Glomerular Filtration Rate (GFR) < lower limit of normal (LLN) using the CKD-EPI equation.
- 13. History of clinically significant cardiovascular, renal, hepatic, neurological (especially seizures), immunological, psychiatric, myopathies, bleeding tendency, respiratory and particularly gastrointestinal (GI) disease, especially peptic ulceration and chronic gastritis, GI bleeding, ulcerative colitis, Crohn's Disease or Irritable Bowel Syndrome, as judged by the Investigator.
- 14. History of additional risk factors for Torsades des Pointe (*i.e.* heart failure, hypokalaemia, family history of long QT syndrome).
- 15. Rare hereditary problems of fructose intolerance, glucose-galactose malabsorption or sucrose-isomaltase insufficiency.
- 16. Any relevant GI complaints within 7 days of dosing.
- 17. Serious adverse reaction or clinically relevant hypersensitivity to any drug or the formulation excipients (Hypromellose [HPMC], sodium lauryl sulphate [SLS], sucrose, croscarmellose sodium and magnesium stearate).
- 18. Presence or history of clinically significant allergy requiring treatment (including asthma, urticaria, clinically significant allergic rash or other severe allergic diathesis), as judged by the Investigator. Hay fever is allowed unless it is active.

DNDi RD 777/34920 DNDi- 0690- 02

Final V3.0/ Date 07 December 2020

Confidential

Page 56 of 109

- 19. Donation or loss of greater than 500 mL of blood within the previous 3 months or more than 100 mL within 30 days prior to signature of informed consent.
- 20. Subjects who are taking, or have taken, any prescribed or over-the-counter drug (including anti-acid drugs) or vitamins/herbal remedies (*i.e.* St. John's Wort and others which are known to interfere with the CYP3A4 and P-gp metabolic pathways) or hormone replacement therapy (HRT) or any drug known to modify the MATE-1/OCT-2 renal transporters (such as, for example, cimetidine, ritonavir, trimethoprim, cisplatin) in the 28 days before IMP administration (or 5 half-lives of the taken drug, whichever is longer). Administration of up to 4 g of paracetamol per day within 7 days of IMP administration is allowed.
- 21. Surgery within 12 weeks prior to Screening, with the exception of appendectomy.
- 22. Any surgery (*i.e.* gastric bypass) or medical condition that may affect absorption of orally administered drugs.
- 23. Failure to satisfy the Investigator of fitness to participate for any other reason
- 24. Breastfeeding and lactating females.

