#### **Treatment Period (Day -2 to Day 12):**

Subjects will be admitted to the clinic in the morning of Day -2 and will remain in the unit until the 48 hours post-last dose scheduled assessments and procedures have been performed (Day 12).

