#### 10.5.3.3 Alcohol Intake

Subjects must abstain from alcohol during the 24 h prior to Screening and the 48 h prior to admission until discharge from the study. Subject must have a negative alcohol screen at admission.

DNDi RD 777/34920 DNDi- 0690- 02

Final V3.0/ Date 07 December 2020

Confidential

Page 59 of 109

From Day -7 to Day -3, the consumption of alcohol will be limited to a maximum of 2 units per day. Any deviation outside this alcohol intake restriction will be assessed on a case by case basis at Investigator's discretion (provided the subject's alcohol intake will not impact in the safety aspects and objectives of the study).

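### Exclusion 6 makes its weekly alcohol limit depend on a urine test taken after instructed abstinence, exclusion 7 leaves the role of smoking history unclear, and two alcohol rules in Section 10.5.3.3 conflict on Day -4 and Day -3

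*Protocol*

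**What the plan says.** Exclusion 6 in Protocol Section 10.4.2 names the group to be kept out as "Regular alcohol consumption in males >21 units per week and females >14 units per week". After defining a unit, it adds "As confirmed by a positive urine alcohol test at Screening or admission".

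Exclusion 7 reads "Current smokers or those who have smoked within the last 12 months with a positive cotinine result at Screening and Admission". Exclusion 8 covers users of e-cigarettes, patches or gums and extends to "those who have used these products within the last 12 months"; it mentions no test. The Synopsis carries the same three criteria.

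Section 10.5.3.3 states "Subjects must abstain from alcohol during the 24 h prior to Screening and the 48 h prior to admission until discharge from the study". Its next paragraph states "From Day -7 to Day -3, the consumption of alcohol will be limited to a maximum of 2 units per day", and then leaves deviations to the Investigator case by case. The Synopsis fixes the timing of admission: "Subjects will be admitted to the clinic in the morning of Day -2".

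Other provisions bear on the point:

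- Inclusion 7 requires a negative urine screen, including alcohol and cotinine, within 28 days before the first dose, and lets the Investigator repeat a positive test.
- The Day -2 re-check in Section 10.4.1 requires a negative alcohol and cotinine screen again.
- Exclusion 4 (abuse history in the past 2 years), exclusion 10 (liver tests above 1.2 ULN), exclusion 23 and inclusion 16 (Investigator's view of fitness) do not depend on the urine alcohol or cotinine result.
- Section 10.4 does not permit deviations from the criteria and calls for adherence to them as specified.

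**The concern.** A limit on habitual weekly intake and a spot urine test measure different things. Making the first conditional on the second, after the subject has been told not to drink, means that the numerical limit may not act on the people it describes. Because Section 10.4 does not permit departures, the literal wording governs, and under exclusion 6 that wording does not deliver its own limit.

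Exclusion 7 raises a related question: is a smoking history within 12 months a ground for exclusion by itself, or only together with positive cotinine results? It joins the two visits with *and*, where exclusion 6 uses *or*, and it treats smokers differently from the nicotine-replacement users in exclusion 8.

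The alcohol windows matter in practice. A volunteer who relies on the 2-unit ceiling on Day -4 or Day -3 breaches the abstinence rule shortly before a Day -2 test that must be negative.

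What is at stake is consistent application of the stated entry limits across the cohorts. No estimate or error rate is involved.

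**Working it through.** No sample size, power or other statistical figure is involved. The check is calendar arithmetic plus a logical comparison of the criteria.

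**Exclusion 6 against inclusion 7 and the Day -2 re-check.** Take a subject whose regular intake is above the limit.

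| Urine alcohol result | Exclusion 6, read literally | Inclusion 7 / Day -2 re-check |
|---|---|---|
| Negative at Screening and admission | Not met: no confirming test | Passed |
| Positive at either visit, not repeated | Met | Failed |
| Positive, then negative on a permitted repeat | Met: a positive test occurred | Inclusion 7 can be passed |

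The first row is the gap. As an illustration, a man drinking 40 units a week is at 40 / 21 = 1.9 times the limit. If he abstains as instructed and tests negative, exclusion 6 does not catch him. The documents do not say how long alcohol stays detectable, so the statement is that he *can* test negative, not that he will. The third row is the only case in which exclusion 6 adds to the inclusion criteria.

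**Exclusion 7.** The phrase "with a positive cotinine result at Screening and Admission" can attach in two ways.

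- *To both groups.* Current smokers and those who smoked within 12 months are excluded only if both tests are positive.
- *To the second group only.* Current smokers are excluded outright, and the 12-month group only if both tests are positive.

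On either reading, a person who smoked within 12 months and tests negative at one visit is not caught. A person positive at either visit already fails inclusion 7 or the Day -2 re-check, unless a permitted repeat is negative. So the look-back adds almost nothing. Sections 10.5.3 and 10.5.4 restrict meals, fluids, alcohol, caffeine, poppy and sesame seeds, grapefruit and similar foods, exercise and blood donation. None instructs abstinence from tobacco or nicotine.

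**Alcohol windows in Section 10.5.3.3.**

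- Start of abstinence: morning of Day -2 minus 48 h = morning of Day -4.
- Days under the 2-unit ceiling: Day -7, -6, -5, -4, -3 = 5 days.
- Days under both rules: Day -4 (from the morning) and Day -3 = 2 of 5 days.
- Largest discrepancy: 2 days x 2 units = 4 units under one rule against 0 under the other. This is an upper bound, because Day -4 is covered only from the morning.
- Sensitivity to admission time: if admission fell at the very end of Day -2, abstinence would start at the end of Day -4, and all of Day -3 would still conflict.

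**The case against.** **Other written grounds exist.** A reader might infer that a site could not exclude a known heavy drinker who tests negative. The documents do not support that. Exclusion 23 and inclusion 16 allow exclusion on the Investigator's view of fitness, and exclusions 4 and 10 cover abuse history and raised liver tests. Using any of these is not a departure from the criteria. What remains is that they replace a stated numerical limit with judgement or with a different measurement.

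**The smoking criterion is not void.** A reader might infer that neither exclusion works because subjects abstain before both tests. The abstinence instruction covers alcohol only. Exclusion 7 can be read to exclude current smokers outright, and cotinine-positive subjects are stopped by inclusion 7 and the Day -2 re-check, subject to the repeat. The repeat allowance also means that exclusions 6 and 7 are not wholly redundant. The sound criticism of exclusion 7 is ambiguity and a look-back with almost no effect. The protocol does not say that smokers were meant to be treated like the users in exclusion 8, so that contrast is a reason to clarify, not proof of error.

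**Two units is a ceiling.** A subject who drinks nothing on Day -4 and Day -3 satisfies both sentences, and deviations go to the Investigator's discretion. This softens the consequence. It does not reconcile the text, because a ceiling of 2 units has no function on days when none is allowed.

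**A link to the stopping rules is speculative.** A reader might infer that heavy drinkers could trigger the ALT/AST stopping rule. That rule needs two subjects above 3xULN, judged clinically significant and IMP related. Entrants must have values no higher than 1.2 ULN and must abstain until discharge. The protocol gives no figure connecting earlier drinking to such rises, so this point does not rest on that consequence.

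**Conclusion.** The point holds as a minor matter of eligibility wording, in three parts.

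1. Exclusion 6, read literally, does not catch a subject above the weekly limit who abstains as instructed and tests negative. This rests on taking the added sentence as a condition, which is its plain sense and the sense that Section 10.4 makes binding.
2. Exclusion 7 is unclear about whether smoking history alone excludes. On both readings its 12-month look-back depends on two positive tests and so adds almost nothing.
3. Section 10.5.3.3 gives conflicting alcohol rules for Day -4 (from the morning) and Day -3: 2 of 5 days and at most 4 units. The Day -3 conflict holds for any admission time on Day -2.

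The effect on the trial is small, because other written grounds for exclusion remain. The number of volunteers affected cannot be estimated from the protocol. No stated figure or planned analysis changes.

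**What to change.** - **Exclusion 6, in Section 10.4.2 and the Synopsis:** make reported weekly intake above the limit a ground by itself and remove the sentence that requires confirmation by urine test. The test requirement stays where it already stands, in inclusion 7 and the Day -2 re-check.
- **Exclusion 7, in both places:** reword it so that it is clear whether smoking history and a positive cotinine result are independent grounds, whether the cotinine clause applies to current smokers, and whether one positive visit is enough or both are needed. If the difference from exclusion 8 is intended, say so.
- **Section 10.5.3.3:** reconcile the abstinence period before admission with the limited-intake period so that each day falls under one rule. Which rule should govern Day -4 and Day -3 is for the sponsor and the investigator to decide.

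The cost is an edit to two criteria in two places and to one restriction. The downside is that a few more volunteers may fail screening on history.

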### Additional Exclusion Criteria for Part C

- 25. Hypersensitivity to iohexol or any of its excipients or to iodine, history of allergic reaction to iohexol, iodine or other contrast media, including cutaneous adverse reactions.
- 26. Manifest thyrotoxicosis.

### To be re-confirmed at Day -2:

- 1. Development of any exclusion criteria since the Screening visit.
- 2. Use of prescription or non-prescription drugs, including vitamins, herbal and dietary supplements since Screening, unless in the opinion of the Investigator and Sponsor's Responsible Physician, the medication will not interfere with the study procedures or compromise subject safety.
- 3. Participation in a clinical study since the Screening visit.
- 4. Donation of 100 mL or more blood since the Screening visit.

### 10.5 Additional Advice and Restrictions for Study Population

### 10.5.1 Sperm Donation

Subjects must not donate sperm from the first dose and for at least 3 months after the last dose of IMP.

### 10.5.2 Contraception

There is a significant risk of drug exposure through the ejaculate (which also applies to vasectomised males) that might be harmful to the sexual partners (both male and female), including pregnant partners of male subjects.

Female subjects who are not of childbearing potential do not need to use any methods of contraception.

DNDi RD 777/34920 DNDi- 0690- 02

Final V3.0/ Date 07 December 2020

Confidential

Page 57 of 109

To prevent pregnancy, **male subjects** (and subject's partner of childbearing potential) must be using condom and also willing to use a highly effective method of contraception or 2 effective methods of contraception, if applicable (unless of non-childbearing potential or where abstaining from sexual intercourse was in-line with the preferred and usual lifestyle of the subject [periodic abstinence (*i.e.* calendar, ovulation, symptothermal, post-ovulation methods) and withdrawal are not acceptable methods of contraception]) from the first dose until 3 months after the last dose of IMP.

#### **Highly effective methods of contraception include:**

- Combined (oestrogen and progestogen containing) hormonal contraception (oral, intravaginal and transdermal) associated with inhibition of ovulation,
- Progestogen-only hormonal contraception (oral, injectable and implantable) associated with inhibition of ovulation,
- Intrauterine device (IUD),
- Intrauterine hormone-releasing system (IUS),
- Bilateral tubal occlusion,
- Vasectomised partner (with the appropriate post-vasectomy documentation of the absence of sperm in the ejaculate). For female subjects on the study, the vasectomised male partner should be the sole partner for that subject.

